## 1. INTRODUCTION

This statistical analysis plan (SAP) describes the statistical analysis methods and data presentations to be used in tables, figures, and listings (TFLs) for Study GS-US-342-1143. This SAP is based on study Protocol Amendment 4 dated 15 June 2018 and electronic case report form (eCRF). Any changes made after the finalization of the SAP will be documented in the clinical study report (CSR).

### 1.1. Study Objectives

The primary objectives of this study are as follows:

- The primary objective of the pharmacokinetics (PK) Lead-in Phase of this study is to evaluate the steady state PK and confirm the dose of SOF/VEL FDC in pediatric subjects with chronic HCV infection.
- The primary objective of the Treatment Phase of this study is to evaluate the safety and tolerability of SOF/VEL FDC for 12 weeks in pediatric subjects with chronic HCV.

The secondary objectives of this study are as follows:

- The secondary objective of the PK Lead-in Phase of this study is to evaluate the safety, tolerability, and antiviral activity of 7 days of dosing of SOF/VEL FDC in pediatric subjects with chronic HCV.
- The secondary objectives of the Treatment Phase of this study are:

To determine the efficacy of SOF/VEL FDC for 12 weeks in pediatric subjects with chronic HCV infection, as assessed by the proportion of subjects with sustained virological response (SVR) 12 weeks after cessation of treatment (SVR12)

To determine the proportion of subjects with SVR 4 and 24 weeks after cessation of treatment (SVR4 and SVR24)

To evaluate the proportion of subjects with virologic failure, including breakthrough/nonresponse and relapse

To evaluate the kinetics of circulating HCV RNA during treatment and after cessation of treatment

To evaluate the emergence of viral resistance to SOF and VEL during treatment and after cessation of treatment

To evaluate the effect of treatment with SOF/VEL FDC on quality of life as measured by PedsQL™ Pediatric Quality of Life survey

To evaluate the effect of SOF/VEL FDC on growth and development of pediatric subjects during and after treatment

To evaluate the acceptability, including palatability, of formulations used in the study

The exploratory objective of this study is as follows:

The logo for CCI (Clinical Care Innovations) is displayed in red, serif font against a black rectangular background.

## 1.2. Study Design

This is an open-label, multi-cohort, two-part study evaluating the PK, safety, and antiviral activity of SOF/VEL FDC in chronic HCV-infected pediatric subjects.

Overall, the study will enroll both treatment-naïve and treatment experienced pediatric subjects with at least 20 and up to 40 treatment experienced subjects. Approximately 200 total subjects will be enrolled as follows:

- Approximately 100 adolescents aged 12 to < 18 years
- Approximately 100 children aged 3 to < 12 years

Subjects will be enrolled in a sequential fashion by 3 age groups: 12 to <18 years old, followed by 6 to <12 years old, and 3 to <6 years old.

Eligible subjects will receive SOF/VEL FDC once daily for 12 weeks.

The schedules of assessments for the study are provided as appendices to the SAP (see Study Procedures Table, [Appendix 1](#)).

### 1.2.1. PK Lead-in Phase

The PK Lead-in Phase will evaluate and/or confirm the age appropriate SOF/VEL FDC dose by analyzing PK, safety, and antiviral activity of SOF/VEL FDC through 7 days of dosing.

At least 17 subjects will be sequentially enrolled into each of the following 3 cohorts:

- Cohort 1: 12 to < 18 years old
- Cohort 2: 6 to < 12 years old
- Cohort 3: 3 to < 6 years old

At least 6 subjects weighing  $\geq 17$  kg

At least 6 subjects weighing  $< 17$  kg

Intensive PK and safety results through Day 7 of each Cohort will be reviewed to confirm the appropriateness of the SOF/VEL FDC dose for that age group as well as to determine the age-appropriate dose to be evaluated in the PK Lead-in Phase of the next age Cohort.

Subjects enrolled in the PK Lead-in Phase will immediately enroll in the Treatment Phase as subjects complete Day 7 of PK Lead-in. Subjects will continue dosing with SOF/VEL FDC with no interruption of study drug administration until the appropriateness of the dose is confirmed by PK and safety data from the PK Lead-in Phase.

Cohort 1 subjects will receive a SOF/VEL FDC 400/100 mg adult tablet or 2 × 200/50 mg tablets (if determined necessary based on SOF/VEL swallowability assessment) once a day for 7 days with intensive PK conducted on Day 7.

Cohort 2 subjects will receive SOF/VEL FDC 200/50 mg tablets once daily. If unable to swallow the tablet formulations, the subjects will receive SOF/VEL FDC 200/50 mg oral granules (4 × 50/12.5 mg packets) for 7 days with intensive PK conducted on Day 7.

Cohort 3 subjects weighing  $\geq 17$  kg will receive SOF/VEL FDC 200/50 mg oral granules (4 × 50/12.5 mg packets) for 7 days with intensive PK conducted on Day 7. Cohort 3 subjects weighing  $< 17$  kg will receive SOF/VEL FDC 150/37.5 mg oral granules (3 × 50/12.5 mg packets) for 7 days with intensive PK conducted on Day 7.

### **1.2.2. Treatment Phase**

Additional HCV-infected children will be enrolled into the Treatment Phase upon confirmation of the appropriateness of the dose from the PK Lead-in Phase. The Treatment Phase will be initiated sequentially by age group as defined in Cohorts 1, 2, and 3 of the PK Lead-in Phase.

Subjects who participated in the PK Lead-in Phase will immediately roll over into the Treatment Phase with no interruption of study drug administration until the appropriateness of the dose has been confirmed by PK and safety results from the PK Lead-in Phase. The first visit in the Treatment Phase for these subjects will be the Week 4 visit.

After dose confirmation in the PK Lead-in Phase of each age group, the same dose will be used in subjects of the corresponding age group enrolled in the Treatment Phase.

### **1.2.3. Study Duration**

The total time to complete all study visits is up to approximately 40 weeks including the following periods:

- 28-day (4-week) screening period
- 12-week treatment period
- 24-week posttreatment period

### **1.3. Sample Size and Power**

With approximately 100 subjects enrolled into the 12 to < 18 years of age group and approximately 100 subjects enrolled into the 3 to < 12 years of age group, a 2-sided 95% exact confidence interval of the SVR12 rate in each age group will extend at most 20%.

## **2. TYPE OF PLANNED ANALYSIS**

### **2.1. DMC Analyses**

An external multidisciplinary Data Monitoring Committee (DMC) will review the progress of the study and perform interim reviews of the safety data in order to protect subject welfare and preserve study integrity. To ensure the best interests of the participants, the DMC will recommend to the sponsor if the nature, frequency, and severity of adverse effects associated with the study treatment warrant the early termination of the study, the continuation of the study, or the continuation of the study with modifications.

The DMC's role and responsibilities and the scope of analysis to be provided to the DMC are provided in a mutually agreed upon charter, which defines the DMC membership, meeting logistics, and meeting frequency.

### **2.2. Final Analysis**

After all subjects have completed through the post-treatment week 24 visit or have prematurely discontinued from the study, outstanding data queries have been resolved, and the database has been cleaned and finalized, the final analysis of the data will be performed.

### **3. GENERAL CONSIDERATIONS FOR DATA ANALYSES**

Analysis results will be presented using descriptive statistics. For categorical variables, the number and percentage of subjects in each category will be presented; for continuous variables, the number of subjects [n], mean, standard deviation [SD] or standard error [SE], median, first quartile [Q1], third quartile [Q3], minimum, and maximum will be presented.

Data collected in the study will be presented in by-subject listings for all subjects in the Safety Analysis Set, unless otherwise specified. All by-subject listings will be presented by subject identification (ID) number in ascending order, unless otherwise specified.

#### **3.1. Analysis Sets**

Analysis sets define the subjects to be included in an analysis. Analysis sets and their definitions are provided in this section. The number of subjects eligible for each analysis set will be provided. Subjects who were excluded from Safety and Full Analysis Sets will be provided in a by-subject listing with reasons for exclusion.

##### **3.1.1. All Enrolled Analysis Set**

All Enrolled Analysis Set includes all subjects enrolled in the study after screening.

##### **3.1.2. Full Analysis Set**

The Full Analysis Set (FAS) includes HCV infected subjects who were enrolled into the study and received at least one dose of study drug. The study drug in this study is SOF/VEL FDC.

This is the primary analysis set for efficacy analyses.

##### **3.1.3. Safety Analysis Set**

The Safety Analysis Set includes all subjects who took at least 1 dose of study drug (ie, SOF/VEL FDC).

This is the primary analysis set for safety analyses.

##### **3.1.4. Pharmacokinetic Analysis Set**

###### **Lead-in Phase PK Analysis Set**

The Lead-in Phase PK Analysis Set includes all PK Lead-in Phase subjects who received at least one dose of study drug and for whom at least one non-missing PK concentration data value is available from the PK Lead-in Phase intensive sampling. This is the primary analysis set for PK Lead-in Phase intensive PK analysis.

## Population PK Analysis Set

The Population PK Analysis Set includes all enrolled subjects who received at least one dose of study drug and for whom at least one non-missing PK concentration data value is available from all types of PK sampling. This is the primary analysis set for the Population PK modeling and PK exposure analyses.

The PK Analysis Set is equivalent to the Population PK Analysis Set.

### 3.2. Subject Grouping

For analyses based on the All Enrolled Analysis Set or FAS, subjects will be grouped according to the treatment to which they were enrolled. For analyses based on the Safety Analysis Set, subjects will be grouped according to the actual treatment received. The actual treatment received is defined as the enrolled treatment except for subjects who received treatment that differs from the enrolled treatment for the entire treatment duration. In this case, the actual treatment received is defined as the treatment received for the entire treatment duration.

Generally speaking, the efficacy analyses will be performed on the FAS by age group and by HCV genotype (1 [further broken down to 1a and 1b], 2, 3, 4, 5, 6, or other, as appropriate), as determined by sequencing or, if sequencing is not available, by LIPA. The primary analysis will be performed on the FAS as described in Section 6.1.

For the safety analysis, because all subjects receive SOF/VEL FDC for 12 Weeks, subjects will be summarized by age group.

For selected analyses, for example, the summary of subject enrollment and disposition, the summary of demographics and baseline characteristics, the summary of responses to the acceptability and palatability questionnaire, and the analysis of Tanner pubertal stage assessment data, please refer to the relevant sections for the detailed description of subject grouping.

### 3.3. Strata and Covariates

This study does not use a stratified randomization schedule for enrolling subjects. No covariates will be included in efficacy and safety analyses.

### 3.4. Examination of Subject Subsets

The efficacy endpoint SVR12 will be analyzed for the following subsets:

- sex (male, female)
- race (black, non-black)
- ethnicity (Hispanic or Latino, non-Hispanic or Latino)
- baseline weight ( $\leq$  median,  $>$  median)

- IL28B (CC, non-CC [further broken down to CT, TT])
- baseline HCV RNA ( $< 800,000$  IU/mL,  $\geq 800,000$  IU/mL)
- baseline alanine aminotransferase (ALT) ( $\leq 1.5 \times$  ULN,  $> 1.5 \times$  ULN)
- prior HCV treatment experience (treatment naive, treatment experienced)
- most recent response to prior HCV treatment (non-response, relapse/breakthrough, Unknown) for treatment experienced subjects
- cirrhosis status (presence, absence, not determined)
- study treatment status (completed study treatment, discontinued study treatment)
- adherence to study drug ( $< 80\%$ ,  $\geq 80\%$ ).

### 3.5. Missing Data and Outliers

#### 3.5.1. Missing Data

In general, missing data will not be imputed unless methods for handling missing data are specified.

For missing last dosing date of study drug, imputation rules are described in Section 3.7.1. The handling of missing or incomplete dates for adverse event (AE) onset is described in Section 7.1.5.2, and for prior and concomitant medications in Section 7.8.

For analyses of categorical HCV RNA data, missing posttreatment HCV RNA data will have the missing data imputed. Missing on-treatment HCV RNA will have the missing data imputed up to the time of the last dose (for on-treatment displays). If the study day associated with the last dosing date is greater than or equal to the lower bound of a visit window, and the value at the visit is missing, the value will be imputed. If the study day associated with the last dosing date is less than the lower bound of a visit window then the on-treatment value at that visit will remain missing.

If a data point is missing and is preceded and followed in time by values that are “< lower limit of quantitation (LLOQ) target not detected (TND)”, then the missing data point will be set to “< LLOQ TND”. If a data point is missing and preceded and followed by values that are “< LLOQ detected”, or preceded by “< LLOQ detected” and followed by “< LLOQ TND”, or preceded by “< LLOQ TND” and followed by “< LLOQ detected”, then the missing value will be set to “< LLOQ detected”. In these situations the data point will be termed a bracketed success; otherwise, the data point will be termed a bracketed failure (ie,  $\geq$  LLOQ detected). If a data point is missing and is not bracketed, the missing data point will also be termed a failure (ie,  $\geq$  LLOQ detected) except for SVR24, which will be imputed according to SVR12 status. Success for SVR12 who have no further HCV RNA measurements collected will be counted as a success for SVR24 due to the high correlation between these 2 endpoints.

For the analyses of continuous HCV RNA efficacy data, when and only when a missing HCV RNA value is imputed as < LLOQ TND or < LLOQ detected according to the imputation rule described above, the corresponding continuous value will be imputed to LLOQ = 1 IU/mL. No other imputation will be performed for continuous HCV RNA data.

In the analysis of the PedsQL™ Pediatric Quality of Life Inventory V4.0 Short Form (SF15) questionnaire, missing data at on-treatment visits and posttreatment follow-up Week 12 (FU-12) visit will not be imputed. Last posttreatment observation carried forward will be used for imputation of missing data at posttreatment follow-up Week 24 visit.

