8.2.2. Data Handling Conventions

Missing data can have an impact upon the interpretation of the trial data. Other than the endpoints discussed below, in general, values for missing data will not be imputed.

For the analyses of categorical HCV RNA data, missing posttreatment HCV RNA data will have the missing data imputed. Missing on-treatment HCV RNA will have the missing data imputed up to the time of the last dose.

If a data point is missing and is preceded and followed in time by values that are “< LLOQ target not detected (TND),” then the missing data point will be set to “< LLOQ TND.” If a data point is missing and preceded and followed by values that are “< LLOQ detected,” or preceded by “< LLOQ detected” and followed by “< LLOQ TND,” or preceded by “< LLOQ TND” and followed by “< LLOQ detected,” then the missing value will be set to “< LLOQ detected.” In these situations the data point will be termed a bracketed success; otherwise, the data point will be termed a bracketed failure (i.e., \geq LLOQ detected). If a data point is missing and is not bracketed, the missing data point will also be termed a failure (i.e., \geq LLOQ detected) except for SVR24, which will be imputed according to the SVR12 status. Success for SVR12 who have no further HCV RNA measurements collected will be counted as a success for SVR24 due to the high correlation between these 2 endpoints.

Where appropriate, safety data for subjects that did not complete the study will be included in summary statistics. For example:

- If a subject received at least 1 dose of study drug, the subject will be included in a summary of adverse events according to the treatment received; otherwise, if the subject is not dosed then they will be excluded from the summary.
- If safety laboratory results for a subject are missing for any reason at a time point, the subject will be excluded from the calculation of summary statistics for that time point. If the subject is missing a predose value, then the subject will be excluded from the calculation of summary statistics for the predose value and the change from predose values.

Values for missing safety laboratory data will not be imputed; however, a missing Day 1 result will be replaced with a screening result, if available. If no pretreatment laboratory value is available, the Day 1 value will be assumed to be normal (i.e., no grade [Grade 0]) for the summary of graded laboratory abnormalities.

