8.4.2. Secondary Analyses

The proportion of subjects with HCV RNA below the LLOQ over time (including SVR4 and SVR24) will be presented in tabular and graphical form. Descriptive summaries and listings will be provided for additional efficacy evaluations of the proportion of subjects who experience virologic failure, serum HCV RNA actual values and change from baseline, quality of life endpoints and other endpoint of interest may include ALT normalization.

Exploratory analyses may be performed to assess the relationship between demographic, baseline characteristics (including baseline viral load, genotype, age, sex, race, ethnicity, baseline ALT level), and antiviral activity (HCV RNA reduction, proportion of subjects with HCV RNA < LLOQ at various time points during and following discontinuation of active therapy).

Details on efficacy analyses will be described in the statistical analysis plan.

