The Pediatric Quality of Life (PedsQL™ SF 15) Questionnaires will be completed by all subjects and their parent/legal guardian up to 24-Week Posttreatment visits. The transformed scale scores (0 to 100 scale) at baseline, EOT, or at Early Termination, if applicable, 12-Week Post-Treatment, and 24-Week Post-Treatment visits and change from baseline, change from EOT to posttreatment will be presented for each of the 4 domains of the SF-15 (physical functioning, emotional functioning, social functioning, and school functioning), the psychosocial health summary (emotional, social, and school functioning domains), and the Total Score. Neuropsychiatric assessment will be based on the psychosocial health summary and domains. Scoring of the SF15 scales will be performed as described in Scaling and Scoring of the Pediatric Quality of Life Inventory™ (PedsQL™) by James W. Varni. A Wilcoxon signed rank test will

be used to explore changes in status from baseline to EOT, or at Early Termination, if applicable, and from EOT to each of the posttreatment time points. Results (p values) will be presented but should be interpreted with caution as multiple endpoints are being tested, and the study has not been powered to test these endpoints. Plot of the mean  $\pm$  SD of change from baseline in SF15 summary scores will be presented.

Drug resistant substitutions will be analyzed as part of the Virology Study Report.

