### 6.4. Changes From Protocol-Specified Efficacy Analyses

There are no changes from protocol-specified efficacy analyses.

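### PedsQL scores are carried forward at posttreatment Week 24 only, with no explanation, no declared change and no observed-data analysis

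*SAP*

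**What the plan says.** SAP 3.5.1 opens with a general rule: "In general, missing data will not be imputed unless methods for handling missing data are specified". For PedsQL it then splits the visits. On the one side, "missing data at on-treatment visits and posttreatment follow-up Week 12 (FU-12) visit will not be imputed". On the other, "Last posttreatment observation carried forward will be used for imputation of missing data at posttreatment follow-up Week 24 visit". No reason is given for treating FU-24 differently.

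The protocol's schedule of posttreatment visits (Appendix 2, Appendix Table 3) places the survey at posttreatment Weeks 12 and 24 and not at Week 4. The only scheduled score that can be carried to FU-24 is therefore the FU-12 score.

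Protocol 8.2.2 states: "Other than the endpoints discussed below, in general, values for missing data will not be imputed". The exceptions it goes on to discuss are HCV RNA, missing Day 1 laboratory and vital-sign values, and PK concentrations below the quantitation limit. PedsQL is not among them. For quality of life, Protocol 8.4.2 plans no test: "Descriptive summaries and listings will be provided for additional efficacy evaluations". The same section adds: "Details on efficacy analyses will be described in the statistical analysis plan".

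SAP 6.2.2 summarises PedsQL scores and changes at each visit. It adds Wilcoxon signed rank tests from baseline to EOT and "from EOT to each of the posttreatment time points", which includes FU-24. It tells the reader to treat the p values with caution because there are several endpoints and the study was not powered for them. SAP 6.4 states: "There are no changes from protocol-specified efficacy analyses".

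**The concern.** One visit of a secondary endpoint follows a different missing-data rule from every other visit of that endpoint. The protocol does not provide for that rule, and the SAP neither justifies it nor lists it as a change.

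A subject with no FU-24 survey but with an FU-12 survey contributes the same EOT-to-posttreatment change twice, once at each visit. The FU-24 row then mixes scores measured at 24 weeks with scores measured at 12 weeks. Its n counts subjects who gave no FU-24 score, and its p value partly repeats the FU-12 result. The SAP asks for no split by which a reader of the tables could see how far this goes.

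At stake is the longest-term quality-of-life result in the trial: a change that is absent at FU-24 could be suggested, or one that is present could be diluted.

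**Working it through.** The documents give no figure to reproduce here. They state neither an expected PedsQL missingness nor an effect size or standard deviation. The text settles whether the rule is a departure. The size can only be shown under assumptions.

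**Step 1: the rule, visit by visit**

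| PedsQL visit | SAP 3.5.1 | Protocol 8.2.2 |
|---|---|---|
| On-treatment | not imputed | not an exception, so in general not imputed |
| FU-12 | not imputed | same |
| FU-24 | carried forward (in practice from FU-12) | same |

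The SAP and the protocol's general convention part only at FU-24.

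**Step 2: which results are touched**

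The FU-24 scores, their changes from baseline and from EOT, and the EOT-to-FU-24 Wilcoxon tests are touched. The baseline-to-EOT and EOT-to-FU-12 tests are not. Four domains, the psychosocial summary and the total make 6 scores. With subject and parent reports that is 6 × 2 = 12, so up to 12 tests per age group are affected if all are run.

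**Step 3: bias in the mean change**

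Let d12 and d24 be the true mean changes from EOT to FU-12 and to FU-24. Let m be the share of analysed FU-24 scores that are carried, with missingness unrelated to the scores. Then:

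- carried-forward mean = (1 − m) × d24 + m × d12
- bias = m × (d12 − d24)

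Illustrations in SD units (assumed values):

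- d12 = 0.5, d24 = 0: bias is 0.10 × 0.5 = 0.05 at m = 10% and 0.20 × 0.5 = 0.10 at m = 20%.
- d12 = 0, d24 = 0.3: bias is −0.03 at m = 10% and −0.06 at m = 20%.
- d12 = d24: bias is zero.

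**Step 4: overstatement of n**

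Let q be the share of subjects with no FU-24 survey, and f the share of those who have an FU-12 survey. The analysed n exceeds the observed n by f × q / (1 − q).

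- f = 1: 0.10 / 0.90 = 11% at q = 10%, and 0.20 / 0.80 = 25% at q = 20%. These are upper limits for the assumed q.
- f = 0.5, q = 20%: 0.10 / 0.80 = 12.5%. Subjects who lack both surveys have no scheduled score to carry.

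**Step 5: effect on the test**

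A simulation of the EOT-to-FU-24 Wilcoxon signed rank test used 100 subjects, close to the roughly 100 planned for each of the two main age groups. Other inputs are assumed: 3,000 runs, normal changes with SD 1, FU-12/FU-24 correlation 0.5, random missingness, every missing FU-24 value having an FU-12 value to carry, and two-sided 0.05. Entries are rejection rates, carry-forward / observed-only.

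| Missing at FU-24 | d12 = 0, d24 = 0 | d12 = 0.5, d24 = 0 | d12 = 0, d24 = 0.3 | d12 = 0.3, d24 = 0.3 |
|---|---|---|---|---|
| 10% | 4.7% / 4.6% | 7.4% / 4.6% | 75% / 80% | 83% / 79% |
| 20% | 4.2% / 4.2% | 16.4% / 5.5% | 65% / 74% | 83% / 73% |

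With no change at either visit, carry-forward does no harm. With a change at FU-12 that has gone by FU-24, it raises false rejection. With a change that appears only by FU-24, it loses power. With equal changes at both visits, it gains apparent power by counting subjects not assessed at FU-24.

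**The case against.** The strongest defence is that the SAP was entitled to do this. The protocol's convention is qualified by the words in general, and Protocol 8.4.2 hands efficacy detail to the SAP. The SAP's own rule allows imputation where a method is specified, and here one is. A reader might infer a breach of a protocol ban, or a false statement in SAP 6.4. The documents do not support that: there is no absolute ban, and the SAP authors could regard the rule as delegated detail. What stands is that the departure is neither explained nor declared.

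Imputing the last visit also has a parallel. Both documents set SVR24 from SVR12 status when it is missing and unbracketed. But that rule is in the protocol and rests on a stated high correlation between the two endpoints. SAP 6.2.2 also separates observed from imputed HCV RNA results and limits the SVR12/SVR24 concordance table to observed data. PedsQL gets none of this.

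Three further inferences go too far:

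- That real change between FU-12 and FU-24 is shrunk by the missing share in a planned result. No FU-12-to-FU-24 contrast is planned. The relevant quantity is the EOT-to-FU-24 bias in Step 3.
- That scores must drift over 12 weeks because the subjects are growing. The documents give no evidence for or against this, and if mean scores are stable the bias is zero.
- That the SAP orders carried scores to be treated as observed. It does not say so. It only specifies no separate handling, and by-subject listings of collected data (SAP 3) should allow the observed surveys to be identified.

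Finally, observed-only analysis came out unbiased because missingness was assumed random. Neither method is shown to be better if dropout depends on quality of life. That is a fair limit on the remedy.

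**Conclusion.** The point holds as a minor one. PedsQL is carried forward at FU-24 alone, contrary to the protocol's general convention and to the SAP's treatment of every other PedsQL visit. There is no rationale, no declared change, no observed-only result and no count of carried values.

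The bias in the mean EOT-to-FU-24 change is m × (d12 − d24) under random missingness. It can go either way, and it vanishes if scores are stable after treatment. At an assumed 10% to 20% missing, n at FU-24 is overstated by at most 11% to 25%, and by less where FU-12 is missing too. The missingness and the effect sizes are assumptions, so the larger simulated distortions show what could happen and are not forecasts.

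The effect is confined to FU-24 PedsQL summaries and to p values that the SAP already labels unpowered. That warning cites multiplicity and power, not imputation. SVR12, safety and PK are unaffected.

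**What to change.** In SAP 3.5.1, remove the FU-24 carry-forward from the main PedsQL analysis, so that FU-24 uses observed scores like every other PedsQL visit. In SAP 6.2.2, report the number observed at each visit beside each summary and test. If carry-forward is kept, show it only as a labelled sensitivity table with the number of carried scores, give a reason for it, and declare it in SAP 6.4.

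The cost is a few lines of SAP text, one added count and at most one extra table, with no new data. The FU-24 row becomes somewhat smaller: about 90 or 80 of 100 subjects at an assumed 10% or 20% missing. Observed-only analysis still assumes non-informative missingness, and the SAP should say so.
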